#### **10.2.3 Blinding and emergency un-blinding**

---

The study participants (patients) and all study personnel, including investigators, personnel assessing outcomes, study nurses, data analysts and treating physicians and nurses, will be blinded to allocation to study drug. Only the non-investigating nurse(s) preparing and administering the study drug at randomisation will be aware of treatment allocation.

Un-blinding will be performed in the event of AEs where knowledge of the type of drug might be of importance to the personnel treating the patients, and in the event of SUSARS. Un-blinding will be performed by non-investigating personnel without competing interest, and the result will immediately be reported to the primary investigator, who will then take the required action(s). Unless unavoidable, other investigators and personnel assessing outcomes should not be made aware of treatment allocation.

### **10.3 Population for Analysis**

---

The following populations will be considered for the analyses:

- Intention to treat (ITT) population: All randomised participants, regardless of protocol adherence.
- Per-protocol population (PP): Includes all subjects who have received study drug

### **10.4 Planned analyses**

---

The main statistical analysis is planned when the last patient has completed the end-of-study visit 6 months after randomisation. Safety analyses will be performed biannually.

Deviation from the original statistical plan will be described and justified in the Clinical Study Report. Amendments to plan can be done until day of database lock.

### **10.5 Statistical analysis**

---

All statistical tests will be performed using a two-sided 5 % level of significance. Continuous efficacy variables will be analysed using independent T-tests for comparisons between the treatment arms and baseline-adjusted ANCOVA for difference in changes. If necessary, values will be log-transformed to meet the assumptions of the tests. All analyses will primarily be analysed according to the intention-to-treat principle. Between-group differences in ordinal categorical variables, such as NYHA class, will be analysed using ordinal logistic regression, whereas the count variables will be assessed by Poisson regression. Demographic, efficacy and safety data will be summarised by treatment group using means, minimums, medians, maximums, interquartile ranges and standard deviations for continuous variables and frequency counts and percentages for categorical variables.

Per protocol analyses will be performed using the same methods as for the intention-to-treat analyses.

**The primary endpoint**, the baseline-adjusted between-group difference in peak oxygen consumption, will be calculated by ANCOVA according to the intention-to-treat principle, the statistical null-hypothesis being that the baseline-adjusted oxygen uptake does not differ between the two treatment arms. Secondary analyses will be made according to the per-protocol-principle.

#### **Key, secondary endpoints:**

The baseline-adjusted between-group difference in the change in i) hand grip strength, ii) normally distributed body composition data, and iii) other normally distributed data will be calculated by ANCOVA. The statistical null-hypotheses are that the changes in these characteristics do not differ between patients allocated to iron isomaltoside and patients allocated to placebo.

NT-proBNP, TnT and CRP at six months will be analysed using Mann Whitney U-tests, the statistical null-hypothesis being that the levels of these biomarkers do not differ between the treatment arms. Regarding quality of life, we specifically plan to assess the between-group number of patients with a minimal clinical difference in the SF36 score.

Secondary per protocol analyses will be performed using the same methods as for the intention-to-treat analyses. Exploratory analyses will be made for efficacy variables stratified by centre.

Safety analyses will include tabulation of type and frequency of all adverse events. Any serious adverse events will be reported with comprehensive narratives. Any value of safety laboratory parameters outside normal ranges will be identified.

Missing data will be omitted from analyses, i.e. there will be no imputation or estimation of missing values. Statistical analyses will be performed in IBM SPSS Statistics version 21 or later.

## **11 Study management**

---

### **11.1 Investigator delegation procedure**

The principal investigator is responsible for making and updating a “delegation of tasks” listing all the involved co-workers and their role in the project. He will ensure that appropriate training relevant to the study is given to all of these staff, and that any new information of relevance to the performance of this study is forwarded to the staff involved.

### **11.2 Protocol adherence**

Investigators ascertain they will apply due diligence to avoid protocol deviations. All significant protocol deviations will be recorded and reported in the Clinical Study Report (CSR).

### **11.3 Study amendments**

If it is necessary for the study protocol to be amended, the amendment and/or a new version of the study protocol (Amended Protocol) must be notified to and approved by the Competent Authority and the Ethics Committee according to EU and national regulations.

### **11.4 Audit and inspections**

Authorised representatives of a Competent Authority and Ethics Committee may visit the centre to perform inspections, including source data verification. Likewise the representatives from sponsor may visit the centre to perform an audit. The purpose of an audit or inspection is to systematically and independently examine all study-related activities and documents to determine whether these activities were conducted, and data were recorded, analysed, and accurately reported according to the protocol, Good Clinical Practice (ICH/GCP), and any applicable regulatory requirements. The

principal investigator will ensure that the inspectors and auditors will be provided with access to source data/documents.

## **12 Ethical and regulatory requirements**

---

The study will be conducted in accordance with ethical principles that have their origin in the Declaration of Helsinki and are consistent with ICH/GCP and applicable regulatory requirements. Registration of patient data will be carried out in accordance with national personal data laws.

### **12.1 Ethics committee approval**

---

The study protocol, including the patient information and informed consent form to be used, must be approved by the regional ethics committee before enrolment of any patients.

The investigator is responsible for informing the ethics committee of any serious and unexpected adverse events and/or major amendments to the protocol as per national requirements.

### **12.2 Other regulatory approvals**

---

The protocol will be submitted and approved by The Norwegian Medicines Agency and the Data Protection Officer (Personvernombudet) at Oslo University Hospital before commencement of the study. The protocol will also be registered in [www.clinicaltrials.gov](http://www.clinicaltrials.gov) before the inclusion of the first patient.

### **12.3 Informed consent procedure**

---

The investigator is responsible for giving the patients full and adequate verbal and written information about the nature, purpose, and potential risks and benefits of the study. Study participants will be informed as to the strict confidentiality of their patient data, but that their medical records may be reviewed for trial purposes by authorised individuals other than their treating physician.

It will be emphasised that study participation is voluntary and that the patient is allowed to refuse further participation in the protocol whenever she/he wants. This will not prejudice the patient's subsequent care. Written informed consent must be obtained for all study participants before enrolment in the study. This will be done in accordance with the national and local regulatory requirements. The investigator is responsible for obtaining signed informed consent.

A copy of the patient information and consent form will be given to the patients. The signed and dated consent forms will be filed in the Investigator Site File binder.

### **12.4 Subject identification**

---

The investigator is responsible for keeping a list of all patients (who have received study treatment or undergone any study specific procedure) including patient's date of birth and personal number, full names and last known addresses.

The patients will be identified in the CRFs by a study-specific, unique identification number.

## **13 Trial sponsorship and financing**

---

The IRONIC trial is an investigator-initiated study supported by an unrestricted grant provided by Pharmacosmos®, who have also provided the study drug. The funding sources have had no role in the design of the study; neither will they participate in the implementation of the trial, in the analyses of the results, or in the decision to publish. The investigators take sole responsibility for the integrity of the data, the writing of the manuscript and the dissemination of the results.

## **14 Trial insurance**

---

The Principal investigator has insurance coverage for this study through membership of the Drug Liability Association.

## **15 Publication policy**

---

Upon study completion and finalisation of the study report the results of this study will either be submitted for publication and/or posted in a publicly assessable database of clinical study results.

The results of this study will also be submitted to the Competent Authority and the Ethics Committee according to EU and national regulations. All personnel who have contributed significantly with the planning and performance of the study (Vancouver convention 1988) may be included in the list of authors. The funding sources have had no role in the design of the study; neither will they participate in the implementation of the trial, in the analyses of the results, or in the decision to publish.

3.1 Preface

Iron deficiency is associated with poor exercise capacity, lethargy and reduced quality of life. Our results show that iron deficiency is prevalent in heart transplant recipients. Cardiac allograft recipients have reduced exercise capacity and quality of life compared with the age and gender matched general population. We assume that some of these symptoms are due to iron deficiency, and hypothesise that intravenous iron supplement will improve peak oxygen consumption, muscle strength, functional capacity, cognition, and health-related quality of life in heart transplant recipients with iron deficiency.

3.2 Purpose of the analyses

These analyses will assess the efficacy and safety of iron isomaltoside in comparison with placebo and will be included in the clinical study report

4 Study Objectives and Endpoints

4.1 Study Objectives

The main goal of this study is to evaluate the ability of a single administration of intravenous iron isomaltoside to increase peak oxygen consumption in cardiac allograft recipients who have iron deficiency defined as serum ferritin < 100 µg/l or ferritin between 100 and 300 µg/l in combination with a transferrin saturation < 20 %.

Secondary objectives are to assess the impact of treatment on: (i) iron stores, (ii) muscle strength, (iii) body composition, (iv) cognitive function, (v) quality of life, (vi) markers of myocardial disease and inflammation, and (vii) safety and tolerability.

4.2 Endpoints

The primary endpoint is the baseline-adjusted peak oxygen consumption as measured on a treadmill exercise test 6 months after study drug administration.

Secondary endpoints:

- The number of patients with absolute or functional iron deficiency
- Muscle strength as measured by a dynamometer hand-grip device
- Body composition
- Cognitive function as assessed by the Cambridge Neuropsychological Test Automated Battery
- Quality of life as assessed by the SF-36 and 5D EuroQoL questionnaires
- N-terminal pro-B-type natriuretic peptide (NT-proBNP)
- Cardiac troponin T (TnT)
- C-reactive protein (CRP)
- Inflammatory and vasoactive peptides.

5 Study Methods

5.1 General Study Design and Plan

This is a balanced, randomised, placebo controlled, double blind, parallel group trial. Eligible patients are randomised 1:1 and allocated to intravenous iron supplement or matching placebo at baseline, after providing written informed consent and performing baseline exams. The patients receive the study intervention immediately after randomisation, and no more than 3 days after performing the baseline tests. The patients then return for efficacy tests 6 months ± 2 weeks after the study intervention.

5.2 Study plan and assessments

Phases	Screening	Baseline	Follow-up	
			3 months	6 months
Informed consent	x			
Confirmation of eligibility	x			
ECG		x		x
Echocardiography		x		
Safety samples ¹		x	x	x
Serum hCG ²	x			
Randomisation		x		
Biobank samples ³		x		x
Measurement of peak oxygen consumption		x		x
Hand grip strength		x		x
Body mass composition		x		x
Cognitive function		x		x
Quality of life		x		x
Registration of adverse events		x	x	x

Study drug infusion

5.3 Inclusion-Exclusion Criteria

Patients will be screened for eligibility upon admittance for routine follow-up at least one year after heart transplantation.

5.3.1 Inclusion criteria

[figure not shown]
The following conditions must apply prior to administering the investigational medicinal product:

- Cardiac allograft.
- Presentation at least one year after heart transplantation.
- Iron deficiency defined as serum ferritin < 100 µg/l or ferritin between 100 and 300 µg/l in combination with a transferrin saturation < 20 %.
- Age between 18 and 80 years.
- Informed consent obtained and documented according to Good Clinical Practice (GCP), and national/regional regulations.

5.3.2 Exclusion criteria

Patients will be excluded from the study if they meet any of the following criteria:

- Anaemia (Haemoglobin < 100 mg/l)
- Haemochromatosis
- Haemosiderosis
- Porphyria cutanea tarda
- Blood dyscrasias or any disorders causing haemolysis or unstable red blood cells
- Decompensated liver disease (Child-Pugh score 7 or higher)
- End-stage renal failure, i.e. eGFR < 15 ml/min or on renal replacement therapy
- Planned cardiac surgery or angioplasty within 6 months
- Planned major surgery within 6 months
- Medical history of unresolved cancer (except for basal cell carcinoma)
- Treatment with systemic steroids more than the equivalent of 10 mg Prednisone/day at the time of informed consent or change in dosage of thyroid hormones within 6 weeks prior to informed consent
- Any uncontrolled endocrine disorder except type 2 diabetes
- Pregnancy
- On erythropoietin analogues
- Known sensitivity or intolerance to iron isomaltoside or other parenteral iron preparations
- Intravenous iron supplement within 6 months prior to inclusion
- On oral iron substitution (unless the subject agrees to stop treatment prior to randomisation)
- Ongoing rejections or infections
- Alcohol or drug abuse within 3 months of informed consent that would interfere with trial participation or any ongoing condition leading to decreased compliance with study procedures or study drug intake
- Intake of an investigational drug in another trial within 30 days prior to intake of study medication in this trial or participating in another trial involving an investigational drug and/or follow-up

5.4 Randomisation and Blinding

Balanced, permuted block randomisation (in a 1:1: ratio for the two study arms) using random block sizes was computed by the Research Support Unit at Oslo University Hospital. A complete, sealed randomisation list containing details of all patient numbers and study group is stored as essential documentation within the Trial Master File in a locked office. Treatment allocation is performed by random draw of sealed, opaque envelopes containing cards marked "iron isomaltoside 20 mg/kg" or "placebo". A nurse who does not participate in the trial or has competing interest regarding study outcomes prepared the envelopes and has exclusive access to the list linking study drug numbers, and batch numbers and expiry dates. The administration of the study drug is performed by nurses who are not part of the study team. The study participants (patients) and all study personnel, including investigators, personnel assessing outcomes, study nurses, data analysts and treating physicians and nurses, are blinded to allocation to study drug.

5.5 Study Variables

Primary endpoint: The primary endpoint, the peak oxygen consumption, will be measured as the three highest ten-second averaged measurements before the termination of exercise. The oxygen consumption is measured in ml/kg/min, meaning that the absolute oxygen uptake (in ml/minute) divided by the patient's weight (in kg) as measured on the day of the test procedure.

Secondary endpoints:

The muscle strength is measured in KG. The baseline-adjusted between-group values will be analysed by ANCOVA, if necessary after log.-transformation of the data.

Quality of life as assessed by the EuroQoL 5D 3L will be assessed as the sum of scores (1-3) for the five questions. The between-group difference will be assessed with the Mann Whitney U-test. Forms with more than one missing value will be discarded, whereas an average value will be imputed for forms with one missing variable. The between-group results of visual analogue scale data, on a scale from 1-100, will be assessed with baseline-adjusted ANCOVA. The scores for the SF-36v2 will be summed up and transformed to norm a based score of (mean \pm standard deviation) 50 ± 10 as recommended for this version. The between-group difference in the physical and mental score components, as well as the sum of the components, will be analysed with baseline-adjusted ANCOVA analyses. If more than 20 % of values are missing, the forms will be regarded as invalid, and the patients with these forms will be excluded from the intention to treat analysis. If 20 % or fewer variables are missing, we will impute mean values derived from the existing values in the same subscore (mental or physical)

6 Sample Size

This trial is designed to assess the effect of intravenous iron on peak oxygen consumption in heart transplant recipients with iron deficiency. We consider an increase in peak oxygen consumption of 1.5 ml/kg/min, equivalent to approximately half a Metabolic Equivalent of Task (MET), to represent a clinically meaningful improvement. An increase in O₂ consumption of 1.5 ml/kg/min is approximately 6 % of the baseline maximal oxygen consumption in our heart transplant recipients.

Forty-four patients in each group provides the trial with an 80 % power at an α of 5 % to show a difference between the groups of 1.5 ml/kg/min at an expected repeat-measurement standard deviation of 2.5 ml/kg/min. To allow for drop-out and to improve the chances of obtaining significance for secondary endpoints, we aim to include 100 patients.

7 General Considerations

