#### **7.1.4 Quality of life**

---

Quality of life will be examined at baseline and at the end of the study using two validated questionnaires; the SF36 and the EQ 5D 3L EuroQoL questionnaire. The SF-36v2 is a 36-item general health-related quality of life instrument that has 36 questions that contribute to 8 domains or scale scores of physical functioning, role-physical, bodily pain, general health, vitality, social functioning, and role-emotional and mental health. The EQ 5D 3L EuroQoL questionnaire consists of 2 pages, the EQ-5D descriptive system and the EQ visual analogue scale. The quality of life questionnaires (in Norwegian) can be found in appendix B.

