7.4 Missing Data

Because the efficacy data are collected twice only, and the endpoint analyses will be baseline adjusted ANCOVA or single point assessments only, there will be no imputation of missing data. However, to elucidate possible biases this method entails, baseline data for patients for whom endpoint data exist will be compared with baseline data for patients who for some reason drop out or are unable to complete both sets of tests. We will also explore if the dropout rate differs between the treatment arms. The extent of missing data will be quantified for each endpoint variable.

We expect few missing baseline covariates and will not employ a strategy to impute missing baseline covariates.

8 Summary of Study Data

The baseline, intention-to-treat population demographics will be presented by columns for each treatment (Placebo, Intravenous iron isomaltoside). All continuous variables will be summarised using the following descriptive statistics: mean \pm standard deviation; median (interquartile range). The frequency and percentages (based on the non-missing sample size) of observed levels will be reported for all categorical measures. All summary tables will be structured with a column for each treatment in the order (Control, Experimental) and will be annotated with the total population size relevant to that table/treatment, including any missing observations.

The sample size of non-missing values for univariable summary statistics may be larger than the sample size of non-missing values in a complete-case analysis used in the primary regression (ANCOVA) analysis.

Table 1

Demographics	Placebo	Intravenous iron
Age – years		
Male gender – no (%)		
Time since HTx – years (IQR)		
Reason for HTx, no (%)		
Ischemic		
DCMP		
GUCH no		
Other no		
Left ventricular ejection fraction		
NYHA functional class, no (%)		
I		
II		
III		
IV		
Body mass index – kg/m ²		

Systolic blood pressure – mmHg

Heart rate – beats per minute

Treatment

Cyclosporine/Tacrolimus

Everolimus

Mycophenolic acid/Azathioprine

Prednisolone

Angiotensin converting enzyme inhibitor

Angiotensin II-receptor antagonist

Loop diuretic

Thiazide

Beta-blocker

Calcium antagonist

Platelet inhibitors

Oral anticoagulants

Proton pump inhibitors

Biochemistry

Haemoglobin – g/l

Creatinine - μ mol/L

Estimated glomerular filtration rate – ml/min/1.73m²

Ferritin – μ g/l (IQR)

Transferrin saturation – % (IQR)

Transferrin receptor (mg/l) % (IQR)

Sedimentation Rate – mm (IQR)

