10.1 Adverse Events

Serious adverse events and adverse events of special interest; pregnancies and adverse reactions to the investigational medicinal products will be reported with comprehensive narratives.

11 Technical Details

Statistical analyses will be performed in IBM SPSS Statistics version 21 or later.

12 Summary of Changes to the Protocol

This Statistical Analysis Plan differs from the protocol (Version 1.4) only with regard to the detail with which the statistical methods and plans for how results are communicated are presented, and the specification of exploratory subgroup analyses of the primary endpoint.

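### SAP 5.5 fills gaps in SF-36 and EQ-5D forms where protocol 10.5 and, read literally, SAP 7.4 allow no imputation, and its SF-36 rule lets at least one blank domain be filled from other domains

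*SAP*

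**What the plan says.** **Item rules.** SAP 5.5 sets one threshold for the SF-36: "If more than 20 % of values are missing, the forms will be regarded as invalid". At or below that threshold, "we will impute mean values derived from the existing values in the same subscore (mental or physical"). No minimum number of answered items per domain is given. For the EQ-5D, the same section discards forms with more than one missing answer and fills a single missing answer with an average.

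**General rules.** SAP 7.4 states that "there will be no imputation of missing data". Protocol 10.5, under the key secondary endpoints, states that "there will be no imputation or estimation of missing values" and that missing data are left out of the analyses. Neither text makes an exception for questionnaire items.

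**Declared differences.** SAP section 12 opens: "This Statistical Analysis Plan differs from the protocol (Version 1.4) only with regard to the detail". The only other difference it names is the specification of the exploratory subgroups.

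**What is scored and analysed.** Protocol 7.1.4 describes the SF-36 as having "36 questions that contribute to 8 domains or scale scores". SAP 5.5 puts the scores on a norm-based scale of "50 ± 10 as recommended for this version" and continues: "The between-group difference in the physical and mental score components, as well as the sum of the components, will be analysed with baseline-adjusted ANCOVA analyses". SAP 9.2.1 compares the proportions of patients who improve or deteriorate by 4 points. It does not name the scale in that sentence, but protocol 10.5 ties the corresponding analysis to the SF-36.

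**The concern.** Two things are wrong.

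First, the rules give different answers for the same form. A returned SF-36 with one blank item is scored and kept under SAP 5.5. Under protocol 10.5 the missing value may not be estimated and drops out. The same holds for an EQ-5D with one blank answer. Quality of life is a named secondary objective, so the plan should settle which forms enter the analysis.

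Second, the SF-36 fill is coarse. Its source is the whole physical or mental subscore and its only limit is for the whole form. A domain that the patient left entirely blank can therefore be built from answers to questions in other domains. The resulting error enters the component score, and through it the ANCOVA and the 4-point responder classification.

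**Working it through.** **Primary sample size, for orientation.** 2 × (1.96 + 0.84)² × 2.5² / 1.5² is about 43.6, so 44 per group, as stated in protocol 10.1 and SAP section 6. Nothing below depends on it.

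**1. The rules side by side, for a returned form with one blank item**

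| Text | SF-36 form | EQ-5D form |
|---|---|---|
| SAP 5.5 | item filled, form kept | item filled, form kept |
| SAP 7.4, read literally | no fill | no fill |
| Protocol 10.5 | no fill or estimate, value omitted | no fill or estimate, value omitted |
| SAP section 12 | no departure declared | no departure declared |

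**2. How much may be missing on a valid SF-36 form**

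Inputs: 36 items and 8 domains (protocol 7.1.4); 20 % limit (SAP 5.5).

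- 0.20 × 36 = 7.2, so at most 7 items may be missing: 7/36 = 19.4 %. Eight items (8/36 = 22.2 %) make the form invalid.
- If every domain had 5 or more items, there would be at least 8 × 5 = 40 items. There are 36, so the smallest domain has at most 4 items, or 4/36 = 11.1 % of the form.
- Since 4 ≤ 7, at least one complete domain can be blank on a form that still counts as valid.
- SAP 5.5 does not say whether its threshold counts items or domain scores. If it counts domain scores, 0.20 × 8 = 1.6, so one whole domain may be missing. The conclusion is the same.

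**3. How far one filled domain can move a component score (illustration)**

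Assumptions not in the documents: a component is the plain mean of four domain scores, each with SD 10 and common correlation r; one domain on one form is blank and is replaced by the mean of the other three; errors are normal.

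- Error in the filled domain: variance = 10² × (1/3 + 2r/3 + 1 − 2r) = 100 × (4/3) × (1 − r).
- Error in the component score: SD = √[100 × (4/3) × (1 − r)] / 4.
- Probability that this error alone reaches 4 points: 2 × [1 − Φ(4 / SD)].

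| r | SD, filled domain | SD, component | P(error ≥ 4 points) |
|---|---|---|---|
| 0.3 | 9.66 | 2.42 | 9.8 % |
| 0.5 | 8.16 | 2.04 | 5.0 % |
| 0.7 | 6.32 | 1.58 | 1.1 % |

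The percentages apply only to forms missing a whole domain. Smaller errors can still carry a patient who is close to the 4-point line across it.

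**4. Would scoring from the remaining domains avoid this?**

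With S the sum of the three observed domains, filling the fourth with S/3 gives (S + S/3)/4 = S/3. Averaging the three available domains also gives S/3. Under this model the two are identical, so scoring a component from its remaining domains is the same cross-domain fill.

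**The case against.** The strongest defence is one of scope. SAP 7.4 argues from the small number of efficacy time points and goes on to discuss patients who drop out or cannot complete both rounds of testing. That reads as a rule about absent assessments, with SAP 5.5 as the specific rule for scoring a form that was returned. Protocol 10.4 also allows the plan to be amended until database lock, and item scoring could be seen as the added detail that SAP section 12 describes. The reading of SAP 7.4 is reasonable, but SAP 7.4 does not state it, and it does not answer protocol 10.5, which rules out estimating missing values without qualification.

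A second defence is that the SAP 5.5 rule is prespecified, applies equally to both arms, and concerns secondary endpoints only. All of that is true and limits the weight of the point. It does not make a cross-domain fill the better choice.

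Three stronger readings are tempting, and the documents support none of them:

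- **Several whole domains may be invented.** The documents give no item count per domain. A split of 4/4/4/4/5/5/5/5 adds up to 36, and two blank domains would then need 8 items, above the limit of 7. Only one domain is shown.
- **Domain-specific effects are blurred.** No separate domain is tested. The planned analyses use the two components, their sum and the 4-point classification, so any harm acts through those.
- **The denominator can be picked after the results are seen.** SAP 5.4 blinds the data analysts. SAP 7.1 requires cleaning, SAP approval and database lock before the code is opened. SAP 7.2.3 requires each patient's population status to be documented before the blind is broken. What remains is a choice that is not settled in the plan, made blinded.

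**Conclusion.** The point holds as a minor one. Protocol 10.5 contradicts SAP 5.5 outright, SAP 7.4 does so on its literal wording, and SAP section 12 leaves the difference undeclared. The SF-36 rule permits up to 7 of 36 missing items and sets no limit per domain, so at least one blank domain can be filled from others. That conclusion rests only on the 36 items, the 8 domains and the 20 % limit.

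The size of the effect on scores rests on assumptions outside the documents: equal weights, SD 10 and correlations of 0.3 to 0.7. On those, the added error in an affected component score has an SD of about 1.6 to 2.4 points and reaches 4 points in about 1 % to 10 % of affected forms. The documents do not say how many forms would be affected; it is probably few. The primary endpoint, its analysis and the sample size are untouched.

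**What to change.** Before database lock:

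1. **SAP 5.5.** Fill a missing SF-36 item only from the same patient's answered items in the same domain, and only when a prespecified minimum is answered. At least half is one possible minimum; it is this review's suggestion and does not come from the documents. Otherwise set the domain to missing, and set any component score that needs it to missing too, rather than computing it from the remaining domains.
2. **SAP 7.4.** State that the no-imputation rule covers missing assessments, and that the item-level scoring rules in SAP 5.5 for the SF-36 and EQ-5D are the exception.
3. **SAP section 12.** List this as a departure from protocol 10.5.

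The cost is a few sentences of SAP text. The downside is that a few more forms may lack a component score than under the current rule.
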